8.8 Early Discontinuation of Patients

Patients may voluntarily withdraw consent from the study at any time. If the patient withdraws consent due to any reasons other than treatment discontinuation (eg, patient moved, patient does not complete visits), all of the final measurements should be performed at the exit visit and recorded on the appropriate eCRF. The eCRF for patient treatment discontinuation should be completed to document patient withdrawal of consent.

If a patient discontinues topiramate treatment, the eCRF for patient treatment discontinuation should be completed to document the reason for discontinuation. The patient should not be

exited from the study, but should be administered BOTOX at the next scheduled office visit (ie, week 12, 24, or 36).

If a patient discontinues BOTOX treatment, the eCRF for patient treatment discontinuation should be completed to document the reason for discontinuation. The patient should then be exited from the study and all of the final measurements should be performed at the exit visit and recorded on the appropriate eCRFs.

If a patient is determined as a loss to follow-up, the eCRF for patient treatment discontinuation should be completed to document the reason for discontinuation.

If a patient must exit the study due to pregnancy or the C-SSRS (ie, the patient answers “yes” to questions 4 or 5 in the suicidal ideation section or “yes” to any question in the suicidal behavior section), the eCRF for patient treatment discontinuation should be completed to document the reason for discontinuation. The patient should then be exited from the study and all of the final measurements should be performed at the exit visit and recorded on the appropriate eCRF.

Notification of early patient discontinuation from the study and the reason for discontinuation will be made to Allergan or Allergan designee and will be clearly documented on the appropriate eCRF.

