8.9 Withdrawal Criteria

Female patients must be withdrawn from the study if they become pregnant (see Section 4.5.1.1). Patients who have replied with “yes” to questions 4 or 5 in the suicidal ideation section or “yes” to any question in the suicidal behavior section of the C-SSRS should not receive any further study treatments, must be withdrawn from the study and should receive appropriate follow-up as in routine clinical practice.

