**Table 3: BOTOX Compliance Formula**

Time to Next BOTOX Injection	BOTOX Compliance Formula
+/- 7 days from the visit schedule	$\text{Min} \left( \frac{\text{Units Injected}}{155 \text{ U}}, \frac{\text{Sites Injected}}{31 \text{ Sites}} \right) * 100\%$
+/- 8 to 10 days from the visit schedule	$\text{Min} \left( \frac{\text{Units Injected}}{155 \text{ U}}, \frac{\text{Sites Injected}}{31 \text{ Sites}}, 0.90 \right) * 100\%$
+/- 11 to 14 days from the visit schedule	$\text{Min} \left( \frac{\text{Units Injected}}{155 \text{ U}}, \frac{\text{Sites Injected}}{31 \text{ Sites}}, 0.80 \right) * 100\%$

+/- 15 or more days from the visit schedule	0%
---	----

For both the BOTOX and topiramate treatment arms, the number and percentage of patients in each compliance rate category (<80%, 80% – 100%, 100% – 120% and >120% as well as <80% and ≥80%) will be reported. If the treatment compliance is less than 80% or greater than 120% and treatment discontinuation is reported at the subsequent office visit, then date of last treatment taken/received from either the eCRF or the eDiary will be the reported as date of discontinuation. Percentages will be calculated from the number of patients who have received treatment in the study period.

If a patient discontinues topiramate treatment, the eCRF for treatment discontinuation must be completed to document the reason for discontinuation. The patient should not be exited from the study, because BOTOX must be administered at the next scheduled office visit (ie, Week 12, 24, or 36).

If a patient discontinues BOTOX treatment, the eCRF for treatment discontinuation must be completed to document the reason for discontinuation and the patient will be exited from the study.

Treatment compliance will be summarized for the Safety Set. Patients will be counted in the treatment arm in which treatment was received. The study drug compliance rate will be summarized using descriptive statistics. Counts and percentage of patients in each compliance rate category will be provided. Denominators for percentages will be the total number of patients who received treatment in each treatment arm and overall.

BOTOX treatment administration by visit, topiramate drug accountability, and topiramate drug accountability per eDiary will be presented in data listings.

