## 9. Safety Analyses

All analyses of safety will be conducted using the Safety Set. All patients will be summarized according to the treatment they actually received, but the subgroup of topiramate patients who initially received topiramate and then switched to BOTOX will be summarized as follows:

- All safety assessments occurring prior to the date of the first dose of BOTOX will be summarized for the topiramate treatment arm.
- All safety assessments except AEs occurring on or after the date of the first dose of BOTOX will be summarized separately for the topiramate + BOTOX subgroup. For all AEs, the total number of patients (N) in each treatment arm will represent the number of patients that received that treatment. A patient may be counted in both treatment arms. The overall total will be the number of patients that received any treatment. The topiramate + BOTOX treatment arm will be a subset of the BOTOX treatment arm and will include patients that received both treatments. Denominators for percentages will be the total number of patients in each treatment arm or overall. Treatment-emergent AEs (TEAEs) include all AEs that start on or after the first dose of study medication up to the final visit, or are present prior to the first dose but increase in severity after the first dose of study medication up to the final visit. For patients who switch from topiramate to BOTOX, TEAEs starting on or after the date of the first BOTOX injection will be counted in the treatment arm that they are related to, as determined by a physician. If the TEAE is related to both treatments or if the relationship is unknown, it will be counted in both treatment arms but only once in the total. The topiramate + BOTOX subset will summarize all TEAEs that occurred after a patient has switched from topiramate to BOTOX.

Statistical hypothesis testing will not be performed on any safety results

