## **9.3. Vital Sign Measurements**

Vital signs will be measured at screening, Day 1, and each subsequent office visit.

Systolic and diastolic blood pressure and pulse rate over 30 seconds should be taken after patients have been at rest (seated) for at least 2 minutes. Blood pressure should be recorded in mmHg. Pulse rate should be measured in beats per minutes. Oral, axillary, or tympanic body temperature should be taken. The same route should be used throughout the study. If oral temperature is taken, the patient should not have any oral intake for at least 5 minutes prior to the measurement. Temperature as Fahrenheit (°F) or Celsius (°C) should be specified on the source document and the eCRF.

Summary tables will be presented for vital sign data by treatment group for patients in the Safety Set. Observed results at each visit will be presented.

All vital sign data will be presented in a by-patient listing.

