## **9.7. Columbia-Suicide Severity Rating Scale (C-SSRS)**

The C-SSRS will be conducted at the screening visit and each subsequent office visit. At screening, patients will be asked about the 12 months prior to the screening visit along with a separate assessment for lifetime prior to the screening visit. For visits after the screening visit, the assessment will be for the time period since the previous visit. The assessments will be summarized for each treatment group using the Safety Set.

Among the questions for each assessment time period (lifetime, prior 12 months, since previous visit) are a set of 10 questions intended to elicit a yes or no response from the patient (as deduced by the investigator site's interview of the patient) and a question (post-screening only) regarding completed suicide. Among those questions are 5 regarding suicidal ideation, arranged in order of increasing severity (1= wish to be dead, 2= non-specific suicidal thoughts, 3= method without intent to act, 4= some intent but without plan and 5= intent and plan). Also included are 6 questions in the suicidal behavior section of the C-SSRS (non-suicidal self-injurious behavior, preparatory behavior, aborted attempt, interrupted attempt, actual attempt, and completed suicide).

C-SSRS data will be summarized separately for the following sets of responses: (1) year prior to screening, (2) baseline as reported under "since screening" at the randomization visit and (3) by visit reported as "since last visit." Overall ideation and behavior responses for the treatment period will be done by taking the most severe response (eg, a yes response at any time point for a specific ideation or behavior question).

Counts and percentage of patients with each answer on the questionnaire will be provided. Summary statistics will include the count and percentage of patients for each of the 11 ideation and behavior categories separately and also overall for any ideation, for any behavior and for any ideation or behavior. Denominators for percentages will be the total number of patients treated in each arm.

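### For patients who switch, SAP 9 tabulates the switch-visit C-SSRS under topiramate + BOTOX although its recall interval contains no BOTOX

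*SAP*

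**What the plan says.** SAP 9 has two rules for patients who start on topiramate and later receive BOTOX. Before the switch date: "All safety assessments occurring prior to the date of the first dose of BOTOX will be summarized for the topiramate treatment arm". From the switch date on: "All safety assessments except AEs occurring on or after the date of the first dose of BOTOX will be summarized separately", under a topiramate + BOTOX subgroup. The split is by date alone. The text I had makes no exception for something measured earlier on the day of the injection. AEs have their own rule, based on physician attribution.

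The switch takes place at a scheduled visit. SAP 7.2 says that "BOTOX must be administered at the next scheduled office visit" and names Weeks 12, 24 and 36; Protocol 8.8 says the same. The safety assessments fall on those visits too. SAP 9.7: "The C-SSRS will be conducted at the screening visit and each subsequent office visit". SAP 9.3: "Vital signs will be measured at screening, Day 1, and each subsequent office visit".

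The C-SSRS is retrospective. SAP 9.7: "For visits after the screening visit, the assessment will be for the time period since the previous visit". The same section plans a by-visit table and an overall treatment-period summary that takes each patient's worst answer, with everyone treated in the arm as the denominator.

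Under Protocol 8.9, patients who answer yes to ideation question 4 or 5, or to any behavior question, "should not receive any further study treatments, must be withdrawn from the study".

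**The concern.** On the switch day the C-SSRS describes a stretch of time before any BOTOX was given, but the date rule files it with a group whose name says that BOTOX was received. The same record leaves the topiramate column, while the patient stays in the topiramate denominator. For C-SSRS yes answers this can only lower the printed topiramate percentage and raise the topiramate + BOTOX percentage. The loss is also selective: it falls on patients who stopped topiramate.

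Vital signs taken on the switch day are filed the same way, although a reading on the day of the injection says little about BOTOX exposure. For these the issue is the label only, and I claim no direction of bias.

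Comparing safety is a stated objective, and suicidality is monitored at every office visit, so the table should attach each answer to the period it describes.

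**Working it through.** The plan gives no figure for this rule, so there is none to reproduce. I applied the rule to the visit schedule.

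**Step 1: where the switch-day record goes.** Let D be the date of first BOTOX. An assessment goes to topiramate if its date is < D and to topiramate + BOTOX if its date is ≥ D. The switch-visit C-SSRS and vital signs have date = D, so they go to topiramate + BOTOX.

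**Step 2: what the switch-day C-SSRS covers.** It covers the interval from the preceding visit to D. BOTOX exposure in that interval is zero. It may hold topiramate at a maintained dose, taper, or time off drug.

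**Step 3: comparison with the SAP's own practice.**
- At Day 1, also a first-dose date, SAP 9.7 treats the C-SSRS as baseline, not as a result on treatment.
- If Day 1 is missing, SAP 4 takes baseline from the closest visit up to and including the first-dose date.
- SAP 9.2 has chemistry drawn from switchers before their first BOTOX. A same-day sample would still be labelled topiramate + BOTOX (chemistry is only listed).
- Protocol 8.9 stops treatment after a serious C-SSRS answer, which presupposes that the interview precedes the injection.

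**Step 4: loss per switcher.** Let k be the number of scheduled post-baseline office visits up to and including the switch visit. The rule keeps k − 1 in the topiramate column, a loss of 1/k.

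| Switch at | k | Kept under SAP 9 | Share lost |
|---|---|---|---|
| Week 12 | 1 | 0 | 100% |
| Week 24 | 2 | 1 | 50% |
| Week 36 | 3 | 2 | 33% |

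**Step 5: loss for the arm, under assumed switch rates.** The documents state no switch rate. Take N = 200 topiramate patients (SAP 4.1), S switchers, mean k among them, three visits for each non-switcher and no other missing visits. Share lost = S / [3(N − S) + kS].

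| Assumed S | All at Week 12 (k = 1) | Equal thirds (mean k = 2) | All at Week 36 (k = 3) |
|---|---|---|---|
| 40 (20%) | 40/520 = 7.7% | 40/560 = 7.1% | 40/600 = 6.7% |
| 80 (40%) | 80/440 = 18.2% | 80/520 = 15.4% | 80/600 = 13.3% |
| 120 (60%) | 120/360 = 33.3% | 120/480 = 25.0% | 120/600 = 20.0% |

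**Step 6: effect on a printed C-SSRS percentage, illustration only.** Assume that 25% of the arm would be due to switch at Week 12, that 5% of patients have any yes answer, and that ideation is unrelated to stopping. Let q be the share of those patients' yes answers confined to ideation items 1 to 3. Printed topiramate rate = 5% − 25% × 5% × q = 5% − 1.25% × q. It lies between 3.75% (q = 1) and 5% (q = 0). If ideation made stopping more likely, the loss would be larger.

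**The case against.** The strongest reply is that little depends on these tables. SAP 9 plans no hypothesis tests on safety. The tolerability hypothesis in Protocol 2.2 rests on AE rates and on discontinuations due to AEs, and the date rule excludes AEs. This stands, and it limits the severity.

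Several stronger readings are tempting, but the documents do not support them.

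- **Serious suicidality is moved away from topiramate.** If Protocol 8.9 is followed, a yes to ideation 4 or 5 or to any behavior item means that no BOTOX is given. There is then no switch date, and the record stays under topiramate. Only negative answers and ideation items 1 to 3 move.
- **The BOTOX column is contaminated.** Non-AE data go to a separate subgroup. The sentence that makes this subgroup part of the BOTOX arm belongs to the AE rules. The subgroup's Week 12 row can hold only switch-day records, so a careful reader could identify those.
- **Vital signs are biased against one arm.** SAP 9.3 plans observed values by visit, and nothing shows a direction. The order of measurement and injection is not stated in the text I had, which lacked the visit procedures and the schedule table.
- **Weight is affected too.** It is measured at each office visit, but I found no post-baseline weight table.
- **The recall interval equals topiramate exposure.** A patient who stops early waits until the next scheduled visit, so part of the interval may be taper or off drug. What is certain is that it contains no BOTOX.
- **The sample-size sources give a switch count.** Non-completion there runs from 12/96 = 12.5% to (170 − 116)/170 = 54/170 = 31.8%, or 25 to 64 of 200. But patients leaving other studies are not switchers in this one, and the 12/96 arm was a combination with propranolol. The last source is also inconsistent: 45/170 = 26.5%, whereas the stated 29.4% fits 45/153.

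**Conclusion.** The point holds in a limited form. SAP 9 states a rule that places the switch-visit C-SSRS, with a BOTOX-free recall interval, under topiramate + BOTOX. A Week 12 switcher then has no scheduled post-baseline C-SSRS in the topiramate column but still counts in its denominator. This is a wrong table entry produced by a stated rule, not a gap in detail.

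The certain part of the size is one office assessment per switcher. The arm-level percentages rest on assumed switch rates and complete visits. The 3.75% to 5% range is an illustration, not an estimate.

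The conclusion assumes that the C-SSRS is read before the injection, as Protocol 8.9 implies, and that its withdrawal rule is followed. Severity is minor to moderate: primary, secondary and AE-based results do not change, but a suicidality table would attribute answers to the wrong period.

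**What to change.** Make these changes before the database lock for the primary analysis after Week 36.

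1. In SAP 9, assign non-AE safety assessments dated up to and including the date of first BOTOX to the topiramate arm, and only later ones to topiramate + BOTOX. Say that the topiramate entry means the pre-switch period, including any taper or off-drug time.
2. In SAP 9.7, state that a C-SSRS answer whose recall interval precedes the first BOTOX injection belongs to the pre-switch period.
3. Show the switch-visit value in the topiramate + BOTOX subgroup as its baseline only. It is then counted as a result once, under topiramate, and never as a post-BOTOX finding.

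The cost is a sentence or two in each section and a change from ≥ to > in the derivation. No new data are needed and no clinical procedure changes. The downside is that a rare assessment made after the injection on the same day would be counted under topiramate.

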2.2 Clinical Hypotheses

[figure not shown]
- BOTOX is more effective than topiramate as measured by the difference between treatment groups in a 50% responder rate (defined as the proportion of patients with a $\geq 50\%$ reduction from baseline in the number of headache days over a 28-day period).
- BOTOX has a superior tolerability profile than topiramate as measured by the difference between treatment groups in the rates of adverse events and discontinuations due to adverse events.
- BOTOX has an acceptable safety profile.

3. Study Design

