### **9.1.1. Incidence of Adverse Events**

All AEs will be summarized for the Safety Set in the manner described in Section 9. Counts and percentage of patients with each type of AE will be provided. Denominators for percentages will be the total number of patients treated in each arm or overall. At each level of patient summarization, a patient is counted once if the patient reported one or more events.

An overview summary of the number and percentage of patients with any TEAE, serious TEAE, study drug-related TEAE, study drug-related serious TEAE, TEAE leading to treatment discontinuation, TEAE leading to study discontinuation, and AE leading to death will be provided by treatment arm.

Treatment-emergent AEs will also be summarized separately for each injection cycle for BOTOX treated patients.

The following summary tables will be repeated for any TEAE, serious TEAE, study drug-related TEAE, study drug-related serious TEAE, TEAE leading to treatment discontinuation, TEAE leading to study termination, and AE leading to death.

Summaries of the total number of TEAEs and the number and percentage of patients with at least one TEAE will be provided by treatment group. The number and percentage of patients and the number of events will also be presented by SOC and PT in descending order from the SOC with the highest total incidence (that is, summed across all treatment groups) to the SOC with the lowest total incidence. If the total incidence for any 2 or more SOCs is equal, the SOCs will be presented in alphabetical order. Within each SOC, the PTs will be presented in alphabetical order. At each level of patient summarization, a patient is counted once if the patient reported one or more events.

All AEs, will be presented in a by-patient listing.

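### Crude TEAE percentages mix unequal and partly undefined times at risk, so equal adverse-event hazards can look unequal in either direction

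*SAP*

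**What the plan says.** Protocol section 2.2 states that BOTOX is better tolerated than topiramate, judged by the "difference between treatment groups in the rates of adverse events and discontinuations due to adverse events".

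The tables that bear on this are defined in the SAP:

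- Section 9 sets the denominator: "For all AEs, the total number of patients (N) in each treatment arm will represent the number of patients that received that treatment". A switcher counts in both columns, and "The topiramate + BOTOX treatment arm will be a subset of the BOTOX treatment arm".
- Section 9.1.1 reports heads: "Counts and percentage of patients with each type of AE will be provided", and "Denominators for percentages will be the total number of patients treated in each arm or overall". Section 9.1.5 uses the same denominator for adverse events leading to treatment discontinuation.
- Before a switch: "All safety assessments occurring prior to the date of the first dose of BOTOX will be summarized for the topiramate treatment arm". After a switch, AEs follow their own rule: "TEAEs starting on or after the date of the first BOTOX injection will be counted in the treatment arm that they are related to". If an event is related to both drugs, or the relationship is unknown, "it will be counted in both treatment arms but only once in the total". Nothing says where an event related to neither drug goes.
- Section 9 runs the TEAE period to the final visit, which is Week 48 for switchers. Section 9.1 stops it before the Week 36 office visit.
- Section 7.1 summarises duration of exposure, but no AE rate uses it. The per-cycle TEAE table in section 9.1.1 covers BOTOX-treated patients only.
- Under section 7.2, topiramate stoppers receive BOTOX at the next office visit (Week 12, 24 or 36), and BOTOX stoppers leave the study.

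**The concern.** The percentage of patients with at least one event rises with the time they are watched. Two such percentages compare tolerability only if the columns cover similar time, and here they need not.

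- **Topiramate column.** All TEAEs count up to a switch. Afterwards only those that pass an open-label causality judgement count.
- **BOTOX column.** It pools randomised patients, planned for 36 weeks, with switchers. Switchers contribute about 36, 24 or 12 weeks of BOTOX time if TEAEs run to Week 48, and 24, 12 or 0 weeks if they stop at Week 36. It also includes patients who stopped BOTOX and left.

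The protocol's background section cites high discontinuation on topiramate because of adverse events, so unequal exposure is foreseeable. The SAP plans no hypothesis test on safety, so these descriptive percentages are the only evidence the plan offers on the tolerability hypothesis. A reader cannot tell how much of a displayed difference comes from the drugs and how much from the length and definition of observation.

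**Working it through.** The documents state no AE rate, switch rate or expected exposure, so there is no figure of the plan's own to reproduce. The check asks what the tables would show if the two drugs had the same AE hazard.

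**Inputs from the documents.** 200 patients per arm; 36 planned weeks for randomised BOTOX; switches at Week 12, 24 or 36; last visit for switchers at Week 48. In the earlier phase 3 BOTOX studies cited for sample size, 514 of 688 patients enter the observed Week 32 rate, so 1 - 514/688 = 25.3% do not. I use 25% as a scenario for BOTOX exits.

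**Assumptions, not in the documents.**
- 36-week risk of a first event, r: 20%, 50% or 70%.
- Fraction of topiramate patients switching, s: 20% to 80%.
- Switch times: either two-thirds at Week 12 and one-third at Week 24, or equal thirds at Weeks 12, 24 and 36.
- BOTOX exits: none, or 25% (half at Week 12, half at Week 24).
- Constant hazard, with switching unrelated to events.

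**Formulas.** Hazard λ = -ln(1 - r)/36 per week; P(t) = 1 - exp(-λt). Each column is the mean of P(t) over its patients.

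**Worked case: r = 50%, s = 40%.** P(12) = 20.6%, P(24) = 37.0%, P(36) = 50.0%.

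Switches two-thirds at Week 12 and one-third at Week 24, no BOTOX exits:
- Topiramate, counted to the switch: 0.6 × 50.0 + 0.4 × (2/3 × 20.6 + 1/3 × 37.0) = 40.4%.
- BOTOX column, N = 200 + 80 = 280, TEAEs to Week 48: switchers average 2/3 × 50.0 + 1/3 × 37.0 = 45.7%, so (200 × 50.0 + 80 × 45.7)/280 = 48.8%.
- BOTOX column, TEAEs to Week 36: switchers average 2/3 × 37.0 + 1/3 × 20.6 = 31.5%, so (200 × 50.0 + 80 × 31.5)/280 = 44.7%.

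With 25% exits, the randomised BOTOX patients fall to 0.75 × 50.0 + 0.125 × (20.6 + 37.0) = 44.7%.

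| Switch times | BOTOX exits | Topiramate to switch | BOTOX column to Week 48 | BOTOX column to Week 36 |
|---|---|---|---|---|
| 2/3 Week 12, 1/3 Week 24 | 0 | 40.4% | 48.8% | 44.7% |
| 2/3 Week 12, 1/3 Week 24 | 25% | 40.4% | 45.0% | 40.9% |
| Equal thirds | 0 | 44.4% | 46.0% | 41.2% |
| Equal thirds | 25% | 44.4% | 42.2% | 37.4% |

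The true hazard ratio is 1 in every row, yet the gap ranges from +8.4 to -7.0 points.

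**Causality attribution.** In the first row, suppose 25%, 50% or all of the post-switch events (to Week 48) are also counted for topiramate. Its figure rises from 40.4% to 44.7%, 48.4% or 54.1%, the last being above the BOTOX column.

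**Whole grid, before attribution.** The BOTOX minus topiramate gap runs from 53.8 - 63.1 = about -9 points (r = 70%, s = 40%, equal thirds, 25% exits, Week 36 end point) to 67.8 - 46.3 = +21.5 points (r = 70%, s = 80%, no Week 36 switches, no exits, Week 48 end point).

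**Exposure-adjusted check.** At r = 50%, λ = 0.01925 per week, and × 52 this is 1.00 first event per patient-year. If events and time share one window, both columns return about 100 per 100 patient-years, a ratio of 1.00.

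**The case against.** A reader might infer that topiramate observation simply ends at the first BOTOX injection while BOTOX is always watched for 36 weeks, so that the topiramate percentage must be understated. The documents do not support this. SAP section 9 exempts AEs from the cut at the switch and keeps counting later events for topiramate when they are related to it, related to both drugs, or of unknown relationship. The BOTOX column includes switchers with shorter BOTOX time and patients who left early. Take 50% switching, all at Week 12, and one first event per patient-year. Topiramate counted to the switch is then 35%, and randomised BOTOX patients alone show 50%. The SAP's pooled BOTOX column with the Week 36 end point is (200 × 50.0 + 100 × 37.0)/300 = 45.6%, and topiramate reaches 50% if all post-switch events are also attributed to it. The sign depends on the rules.

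Other points on the plan's side have force:

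- A patient who stops topiramate for an adverse event is already in the any-TEAE row, so shorter follow-up loses nothing there. The constant-hazard model ignores this.
- Events may cluster early, plausibly during the four-week titration, which would shrink the gap.
- AE-related discontinuation is less affected, because stopping the drug is itself the event.
- Exposure is summarised, event counts accompany patient counts, and no safety test is planned.
- Protocol section 7.3.3 (Safety Analyses) is not visible, so an exposure-adjusted rate there cannot be excluded.

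These limit the size and remove any claim about direction. They do not make the columns comparable: SAP section 9 is visible and contains neither a common window across arms nor a rate that uses exposure.

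**Conclusion.** The concern stands as one of interpretability, with direction unknown. The planned TEAE percentages rest on time at risk that differs between columns and is partly undefined, because the two TEAE end points conflict and post-switch events follow a causality rule. With equal constant hazards the artefact runs from about -9 to +21.5 points before attribution. That range depends wholly on the assumed event risks, switch fractions and timings, and BOTOX exits; clustering of events early in treatment would narrow it. General TEAE incidence is exposed to the problem, and AE-related discontinuation less so. The primary efficacy analysis is untouched. The change is worth making because a stated clinical hypothesis depends on these tables and the remedy is cheap.

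**What to change.** 1. In SAP section 9.1.1, add a table by randomised arm of TEAEs, and of AEs leading to discontinuation, with onset from Day 1 up to but not including treatment at the Week 12 visit. Name it the main between-arm tolerability comparison. Planned follow-up is equal in this interval, no patient has yet switched, and no causality rule is needed.
2. Reconcile the TEAE end points in SAP sections 9 and 9.1, and state where a post-switch TEAE related to neither drug is counted.
3. Beside the overview percentages, add exposure-adjusted incidence: patients with a first event per patient-year, with one window for events and time. For topiramate the window runs from first dose to first BOTOX injection or exit. For BOTOX it runs from first injection to exit, with randomised BOTOX patients and switchers shown separately.

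The existing tables can stay. The cost is one extra table and a few columns, from dates the study already records. There are two limits. The Week 12 table does not capture later events. If events cluster early, dividing by shorter topiramate time would raise the topiramate rate, so the exposure-adjusted figures should support the Week 12 table and not replace it.
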